#### Exclusion Criteria

1. Allergy to opiates 2. Chronic pain other than the primary indication for surgery 3. Psychiatric illness 4. History of substance abuse problem including alcohol &/or cannabis 5. BMI > 35 6. Subjects under 18 years of age. 7. Subject without the capacity to give written informed consent. 8. Female subjects who are pregnant

Is eligibility based on age, gender, pregnancy/childbearing potential, social/ethnic group, or language spoken (e.g., English Speakers only)?

Yes

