Attempts have been made with various agents to reduce the development of tolerance and hyperalgesia following remifentanil. Postoperative hyperalgesia and its prevention has been studied with ketamine[10, 11, 15-36], Magnesium [12, 34, 37], Gabapentin[16], Clonidine[19, 38], Lornoxicam [18], Dextromethorphan [39], Paracetamol [40, 41], Morphine [42], Dexmedetomidine [43], Adenosine [44, 45], COX inhibitors [46, 47], Amantadine [48], Nitrous oxide [49], Fentanyl [50], Pregabalin [51], Buprenorphine [52], Midazolam [53], Dexamethasone [36]. Relevant to our current hypothesis is the report that concomitant administration of ultra-low dose naloxone [13] and naltrexone [54] with remifentanil prevented OIH. However, there are no studies on reducing the adverse effects of remifentanil with ultra-low dose naloxone in human subjects. While the traditional role of opiate antagonists have been in cases of opioid overmedication, recent evidence is emerging regarding their use in pain management. Gan et al. 1997 used an ultra-low dose naloxone infusion (0.00025 mg/kg/h or 0.001 mg/kg/h) in postoperative patients receiving IV morphine via a patient-controlled analgesia (PCA) device. Good pain relief was experienced in all groups, however consumption of PCA morphine was significantly reduced in patients that received the lowest infusion of naloxone and opioid-induced side effects (nausea, vomiting, pruritus) were reduced by naloxone at both dose.

Describe the primary outcome variable(s), secondary outcome variables, and predictors and/or comparison groups as appropriate for the stated study objectives/specific aims:

The primary outcome variable of the study will be to determine the occurrence of OIH in high dose remifentanyl treatment group compared to a low dose Remifentanyl group and a high dose Remifentanyl dose with ultralow dose naloxone. OIH will be determined by assessing evoked pain thresholds. Secondary outcomes will include verbal assessment of overall pain levels via validated standard pain questionnaires and post-operative opioid consumption to determine presence of opioid analgesic tolerance. The predicted outcome is that ultralow dose naloxone will attenuate the development of remifentanyl-induced OIH. Primary outcome: Mechanical pain threshold, determined by von Frey filaments, around the incision site at 24 and 48h post-surgery. Primary hypothesis: The mechanical pain thresholds at 48h in the HN group is higher than in the HI group. Secondary

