hypotheses: 1. The mechanical pain thresholds at 48h in the LO group is higher than in the HI group. 2. The mechanical pain thresholds at 24h in both HN and LO group is higher than in the HI group. Secondary outcomes: - Opioid consumption required to control pain over the first 24 and 48h post-operatively. - Cold pressure test for pain threshold and pain tolerance - VAS pain scores measured prior to surgery and at 4, 8 and 12h after extubation and again at 24h and 48h post-operatively. - McGill short form questionnaire to be filled out prior to surgery and at 48h post-operatively - Brief Pain Inventory questionnaire to be filled out prior to surgery and at 48h post-operatively Other data collected will include a baseline history questionnaire (for demographics, age, sex, weight, income level) and the Public Health Questionnaire (PHQ-9) to measure depression as mood greatly influences pain perception. The PHQ-9 will be used to determine whether groups have been stratified appropriately.

List up to ten relevant references/articles to support the rationale for the research:

1. Bekhit, M.H., Opioid-induced hyperalgesia and tolerance. *Am J Ther*, 2010. 17(5): p. 498- 510. 2. Lin, S.L., et al., Co-administration of ultra-low dose naloxone attenuates morphine tolerance in rats via attenuation of

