kept in the research folder, which is kept in the hospital or shredded when it is not needed. If subject data is kept on a computer, the data will only be stored on hospital computers. Subject information will not be shared beyond the IRB approved research team as listed in Section 2 of this protocol narrative. Once consented, the subjects will be randomized by the study team into one of the three study groups: (1) low dose remifentanyl, (2) high dose remifentanyl combined with ultra-low dose naloxone or (3) high dose remifentanyl combined with placebo. The randomization list will be prepared before the study starts using a random number table generator and the study coordinator will obtain the information for each subject after consent. Personnel directly involved in subject care will be blinded as to naloxone or placebo administration. The pain assessors (second blinded group) will be blinded. Surgical procedures will not be altered and subjects will still receive standard subject care. Following consent, a packet of questionnaires (includes baseline questionnaire, Public Health Questionnaire (PHQ-9), VAS, McGill Short Form, Brief Pain Inventory) will be provided to subjects by study staff. All subjects will be required to complete a baseline questionnaire to obtain subject demographics prior to surgery. Opioid-induced hyperalgesia OIH will be measured by determining experimentally induced pain thresholds and clinically meaningful outcomes of pain via validated pain questionnaires and post-operative opioid consumption. These outcomes have previously been used and validated to assess remifentanyl-induced hyperalgesia; pain thresholds to cold and static mechanical stimulation are the most common pain modalities altered by remifentanyl infusion. Experimentally induced pain will be performed in pre-op by quantitative sensory testing via von Frey filaments applied in ascending order to the dorsal surface of the subject's non-dominant hand and 5cm from the incision site. Subjects will be instructed to indicate when stimulus produces a painful sensation as well as when the stimulus becomes unpleasant. In addition to determination of mechanical pain thresholds, cold pain threshold and tolerance will be determined. Subjects will be instructed to immerse their hand in a bucket of ice water and indicate when they first experience a painful sensation (threshold) and to remove their hand from the ice water when they can no

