 Subjects screened for inclusion/exclusion criteria Study introduction  
 during surgical consult visit Subjects provided with consent form and study  
 information sheet 2 Lab Visit Initiate subject consent Hamilton Rating  
 Scale, VAS, McGill Pain Questionnaire, Brief Pain Inventory Finalize Consent  
 3 Pre-Surgery Subject is greeted in preop area Von Frey Testing, Cold  
 Pressor Test, Opioid Consumption Pre-surgery medication: standard-of-  
 care 4 Surgery Group 1 (LO): Induction dose per anesthesiologist (no  
 ketamine); Maintenance: 0.1mcg Remifentanyl Group 2 (HI): Induction dose  
 per anesthesiologist (no ketamine); Maintenance: 0.4mg Remifentanyl +  
 Saline Group 3 (HN): Induction dose per anesthesiologist (no ketamine);  
 Maintenance: 0.4mg Remifentanyl + 0.004mcg/kg/min Naloxone 5 Post-  
 Surgery Post-surgery medication: standard-of-care @4H, @8H, @ 12H: VAS,  
 Opioid Consumption @24H: VAS, Von Frey Testing, Cold Pressor Test,  
 Opioid Consumption @48H: Hamilton, VAS, McGill, Brief Pain Inventory,  
 Von Frey, Cold Pressor, Opioid Consumption UCI IRB

Provide precise definitions of the study endpoints and criteria for evaluation; if the primary outcomes are derived from several measurements (i.e., composite variables) or if endpoints are based composite variables, then describe precisely how the composite variables are derived:

see above

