### **Statistical Considerations**

Is a statistical analysis plan appropriate for this qualitative study design?

Yes

Describe the statistical methods for the stated specific aims and hypotheses. Your analysis plans should match the stated study specific aims and hypotheses:

For the primary outcome, the 2-sample t-test will be applied to compare the difference in mechanical pain thresholds at 24 and 48h between HN and HI group, and between LO and HI group. For the secondary outcomes, the continuous variables will also be analyzed using 2-sample t-test to identify the difference between HN and HI group, and between LO and HI group. The mean level and corresponding 95% confidence interval (CI) will be

obtained for each study group. The categorical outcomes will be analyzed using the chi-square test and the odds ratio (compare to HI group) and corresponding 95% CI will also be obtained.

Describe the statistical method(s) that will be used to analyze the primary outcome(s) or endpoints:

see above

If appropriate describe secondary or post hoc analyses of primary outcome(s) or other exploratory analysis and if necessary, provide a breakdown of the methods used per outcome or endpoint:

Secondary outcomes: - Opioid consumption required to control pain over the first 24 and 48h post-operatively. - Cold pressure test for pain threshold and pain tolerance - VAS pain scores measured prior to surgery and at 4, 8 and 12h after extubation and again at 24h and 48h post-operatively. - McGill short form questionnaire to be filled out prior to surgery and at 48h post-operatively - Brief Pain Inventory questionnaire to be filled out prior to surgery and at 48h post-operatively

**Sample Size Determination:** Explain how the overall target sample size was determined (e.g., power analysis; precision estimation), providing justification of the effect size for the primary outcome based on preliminary data, current knowledge/literature and/or cost consideration; if appropriate, provide sample size justification for secondary outcomes. Power analysis should (at least) match the primary outcome/endpoint:

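### Pre-operative opioid intake is listed as collected but is not used when post-operative opioid consumption is compared, which costs precision and leaves chance imbalance uncorrected.

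*Combined protocol and SAP*

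**What the plan says.** **Who can enter.** The Exclusion Criteria rule out "Chronic pain other than the primary indication for surgery". Chronic pain from the spine condition itself is therefore admitted. The criterion nearest to opioid use is "History of substance abuse problem including alcohol &/or cannabis". Nothing listed excludes prescribed opioid use.

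**What is recorded before surgery.** Step 3 (Pre-Surgery) of the schedule under Study Design includes opioid consumption beside the sensory tests: "Pressor Test, Opioid Consumption Pre-surgery medication". No look-back window, unit or dose conversion is given.

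**What is compared.** Background & Purpose of the Research lists as a secondary outcome "Opioid consumption required to control pain over the first 24 and 48h post-operatively" and gives it a mechanistic reading: "post-operative opioid consumption to determine presence of opioid analgesic tolerance".

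**How it is compared.** Statistical Considerations states: "For the secondary outcomes, the continuous variables will also be analyzed using 2-sample t-test to identify the difference between HN and HI group". The same test is planned for LO against HI. No covariate, change score or subgroup is named. On allocation, Study Design says: "The randomization list will be prepared before the study starts using a random number table generator". It describes no stratification by opioid use.

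**The concern.** A patient who takes opioids daily before spinal fusion is likely to need more opioid afterwards in any arm. If such patients are a sizeable part of the sample, pre-operative intake is a strong predictor of the very quantity used to judge tolerance.

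Leaving it out has two consequences. The spread between users and non-users stays in the residual variance, so the HN-HI and LO-HI differences are estimated less precisely than the scheduled data would allow. And if the arms happen to differ in their share of users, the unadjusted difference in means carries that gap with nothing in the analysis to correct it. At stake is how readable one secondary outcome is.

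**Working it through.** **Inputs from the documents.** Sample Size Determination gives 105 recruited (35 per group), 96 expected for analysis (32 per group), two-sided alpha 0.05, and 80% power at an effect size of 0.71 or 90% at 0.82. The IRB closing form reports 8 enrolled and no analysis yet.

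**Inputs assumed.** The share of pre-operative opioid users is p = 0.3 to 0.5. Users' excess post-operative consumption is k = 1 to 1.5 SD, measured within the user and non-user strata. The documents give neither figure.

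**1. The plan's own figure.** Noncentral-t power at 32 per group is 79.8% for 0.71 and 89.8% for 0.82. The stated power reproduces and is not in dispute.

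**2. Validity of the unadjusted test.** Trials were simulated at 32 per arm (40,000 runs per setting), with 20-50% users and an excess of 1-2 SD. The mean bias was at most 0.002 SD and the type I error 4.9-5.0%. The planned t-test is valid.

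**3. Chance imbalance.** With 32 per arm, 3 patients are 9.4 points and 4 are 12.5 points, so a gap of at least 10 points needs a difference of at least 4 users. From two independent binomials the exact probability is 33.9% at p = 0.3 and 38.2% at p = 0.5. A normal approximation with SD = sqrt(2p(1-p)/32) = 0.115 or 0.125 gives 38% and 42%, which is too high because it ignores the discreteness.

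**4. Variance explained and power.** R² = p(1-p)k² / (1 + p(1-p)k²). Adjusted effect = 0.71 / sqrt(1 - R²). Equivalent gain in patients = 1/(1 - R²) - 1. Power is at 32 per arm, two-sided 0.05.

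| p | k | R² | Adjusted effect | Power, adjusted | Gain in patients |
|---|---|---|---|---|---|
| 0.3 | 1 | 0.21/1.21 = 17% | 0.78 | 87% | 21% |
| 0.5 | 1 | 0.25/1.25 = 20% | 0.79 | 88% | 25% |
| 0.3 | 1.5 | 0.4725/1.4725 = 32% | 0.86 | 92% | 47% |
| 0.5 | 1.5 | 0.5625/1.5625 = 36% | 0.89 | 94% | 56% |

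The unadjusted comparison has 80% power in every row. Spending one degree of freedom on the covariate (61 instead of 62) changes these powers by less than 0.1 point.

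**5. The trial as it closed.** With 8 participants, three group means and one slope, ANCOVA leaves 8 - 3 - 1 = 4 residual degrees of freedom. Imbalance is also more likely. Assuming 3 against 3 patients, the probability that two arms have different numbers of users is 1 - 0.349 = 65% at p = 0.3 and 1 - 0.3125 = 69% at p = 0.5.

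**The case against.** A reader might infer that tolerance present at entry is counted as remifentanil-induced tolerance. The documents do not support that. Patients are randomised and the inference is a difference between groups, so tolerance at entry is balanced in expectation. Chance imbalance is already reflected in the t-test's standard error, and step 2 shows neither bias nor inflated type I error. The unadjusted analysis is inefficient, not invalid. This part of the objection stands in full.

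Three further points also stand:

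- The 0.71 effect is not stated for opioid consumption. The form asks that the power analysis match the primary outcome, which is the von Frey threshold. Together with the assumed p and k, this makes the power gain an illustration.
- Availability of the covariate is not assured. Step 3 names the item without window or unit, so it could mean habitual intake or only doses taken that day. The timing table under Study Design is broken in the available text. Its opioid consumption row shows five marks, as many as the post-operative times, so it cannot confirm pre-operative recording.
- The figures in steps 3 and 4 belong to 32 per arm and cannot be reached with 8 participants.

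It is also tempting to extend the covariate to the von Frey analysis. No calculation here supports that, so it is not part of this point.

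What the objection does not remove is that a baseline value on the schedule, probably prognostic for this outcome, has no role in the analysis or, as described, in the allocation.

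**Conclusion.** The point holds as one about efficiency and chance imbalance in a secondary outcome. Prescribed opioid users are eligible, pre-surgery consumption is on the schedule, and the planned comparison ignores it. At the planned size, the assumed ranges for p and k imply a 34-38% chance of a 10-point or larger gap in users between two arms. They also imply that 17-36% of the outcome variance could be removed, which would take power from 80% to about 87-94% at the illustrative effect of 0.71. If users are rarer, or differ less from non-users, the gain is smaller. The stated sample size calculation is unaffected. For the data actually collected, the lesson concerns reporting: with 8 participants, raw group means of opioid consumption cannot carry a conclusion about tolerance.

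**What to change.** In the statistical methods, replace the two-sample t-test for 24h and 48h opioid consumption by ANCOVA with pre-surgery opioid intake as a prespecified covariate. Beforehand, define that intake (look-back window and one common dose unit) and confirm that the data collected at step 3 support the definition.

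For the 8 participants enrolled, ANCOVA is barely feasible. Report post-operative consumption descriptively by pre-operative opioid use, and draw no tolerance conclusion from raw group means. The closing form says the analysis has not been done, so this can still be settled before results are submitted.

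The cost is small: a definition to write, a check of the collected data, a change of analysis wording, and one degree of freedom in the model.

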#### Limited Eligibility Factors (Special Populations)

1. Click "Add Line" button above Limited Eligibility Factors Table to add a special population
  - a. To change visibility of columns, click "Columns" button above Limited Eligibility Factors Table and select which Column rows to view.
2. Identify the special populations and provide a scientific rationale. Add additional rows, as needed.

Eligibility Limited to the Following Factors

Age

Specify the rationale for this group:

Subjects under the age of 18

Eligibility Limited to the Following Factors

Pregnancy/Childbearing Potential

Specify the rationale for this group:

pregnant female subjects will be excluded from this study due to concerns regarding consent/assent possible unknown risks and the fact

concerns regarding consent, access, possible unknown risks and the fact that these patient groups are not typically among those patients recruited for spinal fusion surgery at our institution.

## Pre-Screening and Determining Eligibility without Informed Consent

Will Identifiable information be obtained for the purpose of screening, recruiting, or determining eligibility of prospective subjects?

Yes

The 2018 Common Rule allows for Pre-Screening activities (i.e., determining if potential subjects may be eligible to participate in research) performed without the written informed consent of the prospective subject or legally authorized representative (LAR). This means that the IRB does not need to grant a waiver of informed consent.

Provide a complete list of the data points, variables, and/or information that will be collected during Pre-Screening (i.e. data abstraction form):

Check here if the list will be submitted as a separate document [i.e. case report form (CRF; eCRF) or data abstraction form]

Check all the Pre-Screening activities that apply:

Study team will screen medical records to determine subject eligibility

Select Medical Record Source (**check all that apply**):

Study team will access their own UCI patients' records and abstract data directly from those records

Will the study team screen stored identifiable biospecimens?

No

Will the study team contact subjects for eligibility or recruitment purposes?

Yes

**REQUIRED!** Submit the pre-screening script in the Attachments Section.

UCI IRB requires the pre-screening script meets the [Recruitment Requirements](#).

## Recruitment Methods

Will this study involve **NO** direct contact with participants (i.e., passive observation of public behavior)?

No

Indicate all methods that will be used to recruit subjects for this study:

Recruitment Method

Clinicaltrials.gov

Specify Where Posted

Type of Space

Confirm that applicable consent documents will include reference to the use of [SONA](#)

Confirm that the [ClinicalTrials.gov](#) statement is in all applicable consent documents

Confirm that the study from the [Center for Clinical Research \(CCR\) Find a Trial web page](#) is registered on [ClinicalTrials.gov](#)

Specify how contact information will be obtained:

Specify how these individuals granted permission and enter HS#:

Examples:

- Individuals who are economically or educationally disadvantaged
- Individuals that have impaired decision-making capacity

- individuals that have impaired decision making capacity
- Physician's own inpatients and/or outpatients
  - Students (undergraduate, graduate, and medical students)
  - Employees of UCI (administrative, clerical, nursing, lab technicians, post-doctoral fellows and house staff, etc.)

**IRB requires that:**

1. Subjects will be approached with an emphasis that participation is voluntary; and
2. Subject will be informed in a caring manner that no matter their decision, it will NOT affect:
  - a. Their relationship with UCI
  - b. How their doctor cares for them as a patient or their care at UC Health in general and/or
  - c. How their instructor grades their participation in the course; and
3. A statement attesting the information above in item b will be included in applicable recruitment and/or consent documents.

Confirm that colleagues may provide a copy of the consent and other UCI IRB approved materials but do not obtain subjects' consent for the research or act as representatives of the investigators

**Confirm that:**

1. The recruitment letter to be signed by the treating physician will be submitted in the Attachments Section
2. Colleagues do not obtain subjects' consent for the research or act as representatives of the investigators

Specify 'Other' recruitment methods:

Specify the precautions taken to avoid compromised objectivity:

Recruitment Method

Other recruitment methods

Specify Where Posted

Type of Space

Confirm that applicable consent documents will include reference to the use of [SONA](#)

Confirm that the [ClinicalTrials.gov](#) statement is in all applicable consent documents

Confirm that the study from the [Center for Clinical Research \(CCR\)](#) Find a Trial web page is registered on [ClinicalTrials.gov](#)

Specify how contact information will be obtained:

Specify how these individuals granted permission and enter HS#:

Examples:

- Individuals who are economically or educationally disadvantaged
- Individuals that have impaired decision-making capacity
- Physician's own inpatients and/or outpatients
- Students (undergraduate, graduate, and medical students)
- Employees of UCI (administrative, clerical, nursing, lab technicians, post-doctoral fellows and house staff, etc.)

IRB requires that:

1. Subjects will be approached with an emphasis that participation is voluntary; and
2. Subject will be informed in a caring manner that no matter their decision, it will NOT affect:
  - a. Their relationship with UCI
  - b. How their doctor cares for them as a patient or their care at UC Health in general and/or
  - c. How their instructor grades their participation in the course; and
3. A statement attesting the information above in item b will be included in applicable recruitment and/or consent documents.

Confirm that colleagues may provide a copy of the consent and other UCI IRB approved materials but do not obtain subjects' consent for the research or act as representatives of the investigators

Confirm that:

1. The recruitment letter to be signed by the treating physician will be submitted in the Attachments Section

